Select patients undergoing elective awake tracheal intubation surgery and randomly assign them to two groups using a random number table. The control group will receive surface anesthesia of the throat using local anesthetic sprayed via fiberoptic bronchoscope, while the experimental group will undergo ultrasound-guided Thyroid Cartilage Plane Block.

The sample size for the study is determined based on the results of a pilot study. The primary outcome measure is the success rate of superior laryngeal nerve blockade. With a statistical power of $1-\beta=0.9$ and a significance level of $\alpha=0.05$, a sample size of $n=25$ is calculated. Assuming a dropout rate of 10%, the final sample size for each group is determined to be 30 cases.

2. Research Methods

The study will clinically evaluate the effectiveness, safety, and ease of performing Thyroid Cartilage Plane Block.

3. Study Steps

Select 60 patients undergoing elective awake tracheal intubation surgery.

Instruct patients to fast (no food or drink) for 8 hours before the procedure.

Upon admission to the operating room, monitor patients' ECG (electrocardiogram), BP (blood pressure), and SpO₂ (pulse oxygen saturation). Establish intravenous access in the upper extremities and administer normal saline solution. Administer a loading dose of dexmedetomidine at 0.5 µg/kg over 5 minutes, followed by an infusion at a rate of 0.3-0.6 µg/(kg·h) and intravenous injection of fentanyl at 0.1 µg/kg. Perform radial artery puncture and catheter placement for invasive arterial pressure monitoring. Use a computer-generated random number table to allocate patients into two groups in a 1:1 ratio. To ensure

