- Continuous use of antiplatelet or anticoagulant medications preoperatively.

- Hoarseness or coughing while drinking water.
- Bronchial asthma.
- Participation in other clinical trials within the previous 3 months before enrollment or current participation in other clinical trials.

3. Study Termination Criteria

The study may be terminated under the following circumstances:

- 1) Any medical condition or event occurs during the study that poses a potential risk to the continued participation of the research subjects.
- 2) Subjects receive anesthetic regimens other than the specified airway surface anesthesia rescue protocol, or if they are unable to complete the trial according to the study protocol for any reason.
- 3) The investigator determines that other circumstances warrant discontinuation from the trial.
- 4) Poor effectiveness of airway surface anesthesia, resulting in the patient's inability to tolerate awake tracheal intubation, or patient refusal to proceed.

Five: Alternative Diagnostic and Therapeutic Methods

In cases where the airway surface anesthesia is ineffective, and patients are unable to tolerate intubation, we will proceed with additional airway surface anesthesia using 2% lidocaine via a fiberoptic bronchoscope through an epidural catheter to enhance airway surface anesthesia.

Six: Assessment Parameters and Timing

Primary Outcome:

Record the comfort score immediately after intubation (5 points: resistance movement of the head or limbs; 4 points: verbal protest; 3 points: severe painful expression; 2 points: slight painful expression; 1 point: no response).

Secondary Outcomes:

1. Record the duration of the blocking procedure (from the start of ultrasound probe positioning to completion of drug administration).

2. Record the following parameters at specific time points (T0: upon entry to the operating room, T1: before insertion of the tracheal tube, T2: immediately after tracheal tube insertion, T3: 5 minutes after successful intubation):

- Mean Arterial Pressure (MAP)
- Heart Rate (HR)
- Ramsay Sedation Score (6 points: unarousable; 5 points: arousable but slow response to stimulation; 4 points: asleep but brisk response to stimulation; 3 points: asleep with a moderate response to command; 2 points: calm and cooperative with orientation; 1 point: anxious, restless, or agitated. Sedation satisfaction is defined as 2-4 points, while oversedation is defined as 5-6 points).

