- Assessment of superior laryngeal nerve blockade effectiveness based on clinical diagnostic criteria: nability to produce high-pitched sounds,

monotone voice.

- Morphological changes in the vocal cords observed during laryngoscopy (e.g., irregular vocal cord surface, wrinkles, malposition, reduced mobility).
- Absence of neural reflex upon touching the mucosa above the vocal cords.
- Meeting two of the above diagnostic criteria indicates excellent superior laryngeal nerve blockade effectiveness.

Eight: Observation, Recording, and Management of Adverse Events

In the event of oxygen saturation dropping below 90% during the experiment, the procedure will be halted. Patients will be instructed to take deep breaths or receive oxygen supplementation via a mask with increased pressure.

Nine: Quality Control and Quality Assurance of the Study

No specific quality control or quality assurance measures are outlined for this study.

Ten: Data Security Monitoring

Clinical research will establish an appropriate data security monitoring plan based on the level of risk. All adverse events will be meticulously documented, appropriately addressed, and tracked until resolution or stabilization. Serious adverse events and unexpected events will be reported to the ethics committee, regulatory authorities, sponsors, and

drug regulatory authorities in accordance with regulations and guidelines. The principal investigator will periodically conduct cumulative reviews of all adverse events, and if necessary, convene investigator meetings to assess the risks and benefits of the study. In double-blind trials, emergency unblinding may be performed if necessary to ensure subject safety and rights.

Eleven: Statistical Analysis

Statistical analysis will be conducted using SPSS 22.0 software. Normally distributed continuous data will be presented as mean \pm standard deviation ($\bar{x}\pm s$), and group comparisons will be made using analysis of variance (ANOVA). Categorical data will be presented as counts or percentages, and group comparisons will be made using the X^2 test. A significance level of $P<0.05$ will be considered statistically significant.

Twelve: Ethical Principles and Requirements for Clinical Research

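### MAP and HR are compared by ANOVA with no baseline term, although a pre-treatment T0 value is scheduled for every patient

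*Protocol*

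**What the plan says.** Section Eleven (Statistical Analysis) opens its rule for continuous outcomes with "Normally distributed continuous data will be presented as mean" and SD, and continues: "group comparisons will be made using analysis of variance (ANOVA"). It names no covariate, change score or repeated-measures structure. The threshold is P<0.05; whether one- or two-sided is not stated.

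Section Six, secondary outcome 2, records MAP, HR and the Ramsay score at four times, beginning "T0: upon entry to the operating room, T1: before insertion of the tracheal tube", then T2 immediately after tube insertion and T3 five minutes after successful intubation.

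Section Three (Study Steps) gives the order of events. Monitoring on admission comes first, followed by dexmedetomidine and fentanyl. Next comes "Perform radial artery puncture and catheter placement for invasive arterial pressure monitoring", then "Use a computer-generated random number table to allocate patients into two groups in a 1:1 ratio", and then the block or spray. T0 is therefore a pre-treatment value in both arms.

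**The concern.** MAP and HR vary widely between patients, and a patient's own starting value usually predicts part of the later value. The plan collects that value but gives it no role in the group comparison.

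Two things are at stake. One is precision: between-patient variation that T0 could explain stays in the error term. The other is interpretation: with 30 per arm, a chance T0 difference carries over into T1 to T3 in proportion to r. Over all randomizations the standard error allows for this. In one particular trial with a visible T0 gap it does not, and adding an adjustment after seeing the gap would be post hoc.

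The word ANOVA can also be read in two ways. As separate ANOVAs, T1 to T3 are compared without T0. As a repeated-measures ANOVA over T0 to T3, the group-by-time term does use T0, as a change from baseline, but the group main effect averages in a time point at which no treatment effect can exist.

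**Working it through.** **Inputs.** From the protocol: 30 per arm, 1:1 allocation, significance level 0.05 (taken as two-sided). Assumed, because the protocol gives no value: a true difference of 0.6 SD, equal SDs at all time points, and a T0-to-follow-up correlation r from 0 to 0.7.

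**The plan's own figure.** The only calculation in the protocol is for the success rate of blockade (power 0.9, n=25, 10% dropout, 30 per arm). The dropout step gives 25/0.90 = 27.8, so 28, which the plan rounds up to 30. The 25 cannot be reproduced because the pilot rates are not given. Nothing is stated for MAP or HR, and this point does not depend on that calculation.

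**1. Validity.** In 20,000 simulated trials per setting with no true effect (r = 0.3, 0.5, 0.7), the unadjusted test rejected in 4.7% to 5.2% and ANCOVA in 4.7% to 5.0%. Both hold their level on average.

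**2. Precision at one time point.** In SD units:
- Unadjusted: variance of the difference 2/30, t test on 58 df.
- ANCOVA: variance (1 − r²) × (2/30 + D²/SSW), t test on 57 df. D is the T0 difference, distributed N(0, 2/30), and SSW is the within-group T0 sum of squares, chi-square on 58 df. Power is averaged over both, so the cost of the covariate is charged.
- Change from T0 (the group-by-time contrast of T0 with one later time): variance 2(1 − r) × 2/30, 58 df.

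| r | Unadjusted | ANCOVA | Change from T0 |
|---|---|---|---|
| 0 | 63% | 62% | 37% |
| 0.2 | 63% | 64% | 44% |
| 0.3 | 63% | 66% | 49% |
| 0.5 | 63% | 74% | 63% |
| 0.7 | 63% | 89% | 84% |

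ANCOVA breaks even with the unadjusted test at r of about 0.13. Its worst loss, at r = 0, is 0.628 − 0.620 = 0.008, or 0.8 points.

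**3. Chance imbalance.** The T0 difference between arms has SE √(2/30) = 0.258 SD. The probability of a gap above 0.5 SD is 2 × [1 − Φ(0.5/0.258)] = 0.053.

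Given a 0.5 SD gap and no true effect, the later difference has mean 0.5r and SE 0.258 × √(1 − r²), while the test still rejects beyond about 1.96 × 0.258 = 0.506. For r = 0.5 the mean is 0.25 and the SE 0.224, so the rejection probability is about 1 − Φ((0.506 − 0.25)/0.224) = 0.126. Simulating the t test itself (100,000 trials per r) gives about 6%, 8%, 12% and 19% at r = 0.2, 0.3, 0.5 and 0.7, against the nominal 5%.

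**4. Repeated-measures reading.** A constant effect at T1 to T3 with none at T0 is diluted in the four-point group main effect to 3/4 = 75%, here 0.75 × 0.6 = 0.45 SD. Averaging also reduces the variance, so dilution alone does not settle the comparison. Assume an equal correlation r among all four times and compare methods that all use the T1 to T3 mean. The variance factors, each multiplied by 2/30, are (1 + 3r)/4 for the main effect, (1 + 2r)/3 + 1 − 2r for the T1 to T3 mean minus T0, and (1 + 2r)/3 − r² for ANCOVA on that mean, with the covariate cost charged as in step 2:

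| r | Four-point main effect | Mean change from T0 | ANCOVA on T1–T3 mean |
|---|---|---|---|
| 0.2 | 77% | 60% | 93% |
| 0.3 | 70% | 66% | 92–93% |
| 0.5 | 58% | 80% | 94% |
| 0.7 | 50% | 95% | 98% |

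ANCOVA is ahead at every r in this table.

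**The case against.** The strongest objection is that model detail belongs in the statistical analysis plan, which is not at hand. Section Eleven is short and generic, names neither MAP nor HR, and does not exclude a covariate or a repeated-measures model. The analysis plan may indeed settle this already. But the protocol does not leave the method open: it names ANOVA for group comparisons, and the point is about that stated choice.

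Second, nothing is invalid; this is a preference for a more efficient test. That is correct, and it sets the level of the point.

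Third, the benefit rests on an unknown r. At r = 0.2 to 0.3 the gain is only 1 to 3 points of power. For MAP, r may be low because T0 precedes sedation and the arterial line. This stands, but the possible loss is under one point.

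Fourth, the 75% dilution is one-sided by itself. With equal correlations, the four-point main effect (77% at r = 0.2) beats ANCOVA at a single time (64%), and the mean change from T0 (80% and 95% at r = 0.5 and 0.7) beats it too (74% and 89%). This is right as far as it goes, but it sets several time points against one. Like for like, ANCOVA does best.

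Finally, a 0.5 SD gap is uncommon, and at low r the conditional error rises only to 6% to 8%. That also stands.

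**Conclusion.** The concern holds, at the level of an optional improvement. The protocol fixes an unadjusted comparison for two outcomes whose pre-treatment value it already schedules. The test keeps its 5% error on average. The loss is between nothing and about 26 points of power (63% against 89%) as r runs from about 0.13 to 0.7, together with a conditional error of about 6% to 19% if the arms differ by 0.5 SD at T0.

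These figures assume 30 analysed per arm, normal data, equal SDs and a 0.6 SD effect; r is not in the protocol. The reach is small: MAP and HR are part of one of ten secondary items, no stated objective is hemodynamic, and neither the primary comfort score nor the sample size depends on them.

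**What to change.** In Section Eleven, for MAP and HR only, replace ANOVA with ANCOVA at each of T1, T2 and T3, adjusted for the patient's own T0 value. Alternatively, specify one mixed model over T1 to T3 with group, time, group-by-time and T0 as covariate. Report T0 by arm descriptively, without a test. Leave the analysis of the other outcomes as it is. If a statistical analysis plan already specifies such a model, align the protocol wording with it.

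The cost is a change of wording, with no extra patients, measurements or procedures. Statistically it is one degree of freedom, and under one point of power if r is near zero. The change should be made before outcome data are seen.

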3. Record the number of cases with reduced voice tone before intubation.

4. Document patient coughing upon contact of the fiberoptic bronchoscope with the vocal cords before intubation (1 point: no response, 2 points: mild cough, 3 points: severe cough).
5. Assess the tolerance of the tracheal tube after successful intubation (3 points: strong resistance requiring immediate general anesthesia; 2 points: restlessness and mild resistance; 1 point: cooperative).
6. Record adverse reactions such as coughing and nausea/vomiting during intubation.
7. Document post-extubation throat pain, voice tone reduction, and voice tone reduction at 24 hours post-operation.
8. Assessment of superior laryngeal nerve blockade effectiveness based on clinical diagnostic criteria:
 - Inability to produce high-pitched sounds, monotone voice.
 - Morphological changes in the vocal cords observed during laryngoscopy (e.g., irregular vocal cord surface, wrinkles, malposition, reduced mobility).
 - Absence of neural reflex upon touching the mucosa above the vocal cords.
 - Meeting two of the above diagnostic criteria indicates successful superior laryngeal nerve blockade.
9. Record adverse reactions such as local anesthetic toxicity, local hematoma at the puncture site, and infections.

10. Record patient satisfaction.

Seven: Efficacy Assessment Criteria

- Record the duration of the blocking procedure (from the start of ultrasound probe positioning to completion of drug administration).
- Ramsay Sedation Score (6 points: unarousable; 5 points: arousable but slow response to stimulation; 4 points: asleep but brisk response to stimulation; 3 points: asleep with a moderate response to command; 2 points: calm and cooperative with orientation; 1 point: anxious, restless, or agitated. Sedation satisfaction is defined as 2-4 points, while oversedation is defined as 5-6 points).
- Patient coughing upon contact of the fiberoptic bronchoscope with the vocal cords before intubation (1 point: no response, 2 points: mild cough, 3 points: severe cough).
- Comfort score immediately after intubation (5 points: resistance movement of the head or limbs; 4 points: verbal protest; 3 points: severe painful expression; 2 points: slight painful expression; 1 point: no response).
- Tracheal tube tolerance after successful intubation (3 points: strong resistance requiring immediate general anesthesia; 2 points: restlessness and mild resistance; 1 point: cooperative).

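### The protocol's two test rules send the ordered comfort score to a chi-square test that ignores order; naming a rank or proportional-odds analysis recovers power at no cost in patients

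*Protocol*

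**What the plan says.** Under Primary Outcome, Section Six (Assessment Parameters and Timing) lists one item, the comfort score just after intubation: "Record the comfort score immediately after intubation (5 points: resistance movement of the head or limbs; 4 points: verbal protest; 3 points: severe painful expression", then two milder steps down to 1, no reaction. The steps are ordered and lower is better.

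Two secondary outcomes in Section Six are three-level ordered scores: cough ("1 point: no response, 2 points: mild cough, 3 points: severe cough") and tube tolerance ("3 points: strong resistance requiring immediate general anesthesia; 2 points: restlessness and mild resistance; 1 point: cooperative"). The six-level Ramsay score is ordered too, but its best values lie in the middle: "Sedation satisfaction is defined as 2-4 points, while oversedation is defined as 5-6 points".

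Section Eleven (Statistical Analysis) gives two rules. The first begins "Normally distributed continuous data will be presented as mean" and leads to ANOVA. The second reads "Categorical data will be presented as counts or percentages, and group comparisons will be made using the X^2 test". It names no rank, trend or ordinal method, and gives no rule for scores that are not normally distributed.

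Section Three (Research Design), in the sample size paragraph, names a different, binary primary outcome: "The primary outcome measure is the success rate of superior laryngeal nerve blockade".

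**The concern.** Section Eleven limits ANOVA to normally distributed continuous data. A five-step behavioural score is neither continuous nor normal, so of the two rules only the chi-square rule fits it. The Pearson chi-square gives the same P value however the five columns are arranged. A better block should move patients towards lower scores. A test with up to 4 degrees of freedom spreads its sensitivity over every possible difference between the arms, including many that have no direction. With 60 patients, a real shift towards comfort could then come out non-significant.

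**Working it through.** **Inputs from the protocol.** Five-level comfort score (Section Six); 1:1 allocation, n = 25 before dropout and 30 per group after, power 0.90, alpha 0.05 (Section Three); ANOVA and chi-square as the only tests (Section Eleven). Two-sided testing is assumed, because the sidedness is not stated, and n = 25 is read as per group.

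**Inputs not in the protocol.** There is no comfort score distribution and no effect on that scale. These are assumed and varied: control-arm percentages for scores 1 to 5 of 20/35/25/12/8, 10/25/30/20/15, 35/30/20/10/5 and 5/15/30/30/20, with a proportional-odds shift. For each cut-point k, odds(score ≤ k) in the block arm = OR × odds(score ≤ k) in the control arm. For example, 20/35/25/12/8 with OR 4 becomes about 50/33/11/4/2.

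**The protocol's own figure.** n = 25 cannot be reproduced, because no success rates are given. It also refers to block success, not to the comfort score. It can still show what size of effect was planned for. The formula is

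n = [1.96·√(2p̄(1−p̄)) + 1.2816·√(p₁(1−p₁)+p₂(1−p₂))]² / (p₁−p₂)².

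For an assumed 0.30 versus 0.74, p̄ = 0.52 and n = (1.96 × 0.7065 + 1.2816 × 0.6344)² / 0.44² = 4.83/0.1936 ≈ 25. The odds ratio is (0.74/0.26)/(0.30/0.70) = 6.6. The other pairs that give 25 are 0.20 vs 0.63 (OR 6.9), 0.40 vs 0.83 (7.2) and 0.50 vs 0.90 (9.3).

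**Power by simulation** (40,000 trials per scenario; range over the four control distributions; 30 per arm):

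| Common OR | Chi-square | Wilcoxon (tie-corrected) | Loss, points |
|---|---|---|---|
| 3 | 36-40% | 61-65% | 24-25 |
| 4 | 55-61% | 79-83% | 22-24 |
| 5 | 69-76% | 89-92% | 16-20 |
| 6 | 78-85% | 94-96% | 11-16 |
| 8 | 88-94% | 98-99% | 5-9 |
| 10 | 93-98% | 99-100% | 2-6 |

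- With 25 evaluable per arm, the loss is 21-26 points at OR 3-5 and 9-15 at OR 8.
- Type I error at 30 per arm is 4.0-4.8% for chi-square and 4.7-5.2% for Wilcoxon, so false positives are not the problem.
- ANOVA on the scores comes within 0-4 points of the Wilcoxon test.
- For three-level scores (control 40/40/20, 25/45/30 and 55/30/15%), chi-square loses 7-12 points at OR 3-5 and 2-7 at OR 8.

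**Sparse tables.** In a separate run with partly different control distributions, at OR 4 and 30 per arm, between 74% and over 99% of tables had more than a fifth of expected counts below 5. The chi-square approximation is therefore strained as well.

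**Worked example** (invented counts, scores 1 to 5): control 6/11/7/4/2, block 15/10/3/1/1.

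- Chi-square: expected counts in each arm are 10.5, 10.5, 5, 2.5 and 1.5. The sum is 3.857 + 0.048 + 1.600 + 1.800 + 0.333 = 7.64 on 4 df, P = 0.106.
- Mann-Whitney: of 30 × 30 = 900 pairs, the control patient scores higher in 510 and ties in 227. U = 510 + 113.5 = 623.5, and the probability of superiority is 623.5/900 = 0.69. The tie-corrected variance is (900/12)(61 − 19,614/(60 × 59)) = 4,159, so z = (623.5 − 450)/64.5 = 2.69, P = 0.007.
- ANOVA: means 2.50 and 1.77, F = 6.79, P = 0.012.

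**Ramsay is different.** With invented counts for scores 1 to 6 of 1/20/6/2/1/0 and 5/14/3/2/4/2, Mann-Whitney gives P = 0.84, although satisfactory sedation (2-4) is 28/30 versus 19/30 (Fisher P = 0.010). Undesirable values at the two ends cancel in a rank test.

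**The case against.** Section Eleven never assigns the comfort score to a test, so the chi-square route is an inference, and an unseen SAP may name another method. If the team treated the points as numbers and ran ANOVA, almost no power would be lost. If block success is the true primary outcome, as Section Three says, chi-square suits it. The larger losses rest on odds ratios of 3 to 5, whereas the only planning figure points to about 6.6-9.3. And every tabulated scenario is a shift, the pattern a rank test is built for. In two other patterns the order reverses: 56% for chi-square versus 38% for the rank test when the change is mainly in the share with no reaction, and 55% versus 5% when only the spread changes.

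Much of this stands as a limit on size. The planning anchor belongs to another endpoint, but if it carried over, the loss would be at the lower end. The reversals are real, but they need something other than the general move towards comfort that the block is meant to produce. The point itself survives. Section Eleven is not silent: it states its rules, and the one that fits an ordered score is a poor one. ANOVA would break the section's own normality condition and treat the five steps as equally spaced. If block success is primary, the point still applies to the comfort, cough and tolerance scores as secondary outcomes.

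**Conclusion.** The concern holds and should be fixed. Read by its own terms, Section Eleven sends the comfort score and the two three-level scores to a test that discards their order. At 30 per arm the loss is about 16-25 points of power for a common odds ratio of 3 to 5, and 2-9 points at 8 to 10. These figures assume a proportional-odds shift and control distributions that the protocol does not supply. The damage reaches the primary analysis only if Section Six's definition of the primary outcome prevails over Section Three's. That conflict is a separate and larger matter: the stated 90% power does not refer to the comfort score at all.

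**What to change.** In Section Eleven, state that the comfort score is compared by the tie-corrected Wilcoxon-Mann-Whitney test, or by a proportional-odds model, and reported as the probability of superiority or the common odds ratio with its 95% confidence interval. Apply the same rule to the cough and tube tolerance scores. Leave Ramsay out of it: at each recorded time point, compare the proportion with satisfactory sedation (2-4) and the proportion oversedated (5-6). Score 1 has no label in the protocol, but it counts as not satisfactory in the first comparison. Keep chi-square for binary outcomes, including block success, with Fisher's exact test where expected counts fall below 5.

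This is a wording change. It needs no extra patients or data, and the methods are in standard statistical software. The costs are an effect measure less familiar than a mean or percentage, and less sensitivity to differences that are not a shift along the scale. The choice should be made before outcome data are seen.

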However, the method of performing nerve blocks through surface anatomy localization has its drawbacks, including inaccurate positioning, low success rates, poor safety, and unsatisfactory outcomes. Some researchers argue that using the thyrohyoid membrane as a target for ultrasound-guided superior laryngeal nerve block can be challenging. Traditional ultrasound-guided superior laryngeal nerve block methods often rely on the thyrohyoid membrane and the superior thyroid artery as ultrasound landmarks, injecting local anesthetic solution beneath the thyrohyoid membrane and adjacent to the superior thyroid artery. However, locating the thyrohyoid membrane and the small superior thyroid artery can be extremely challenging, especially for beginners. Even experienced clinicians, despite their familiarity with anatomy and skill, can struggle to identify these structures under ultrasound. Therefore, there is a pressing need for simpler, more precise, and easier-to-locate methods of superior laryngeal nerve block in clinical practice.

In our preliminary research, while performing superior laryngeal nerve block, we observed that the injected solution could spread along the surface of the thyroid cartilage plate, extending towards the thyrohyoid membrane. Given that the solution could reach the superior laryngeal nerve from the surface of the thyroid cartilage, we propose that injecting

local anesthetic solution on the surface of the thyroid cartilage can effectively block the superior laryngeal nerve, a technique we refer to as "Thyroid Cartilage Plane Block." This method offers the advantage of easy identification of the thyroid cartilage under ultrasound, making it more convenient to perform than traditional methods. Therefore, this study aims to investigate the clinical effectiveness and safety of superior laryngeal nerve block through surface injection of local anesthetic solution on the thyroid cartilage in patients undergoing general anesthesia with endotracheal intubation.

Two: Research Objectives

1. Primary Objective: To evaluate the effectiveness of ultrasound-guided Thyroid Cartilage Plane Block for superior laryngeal nerve blockade.
2. Secondary Objectives: To assess the safety and ease of performance of ultrasound-guided Thyroid Cartilage Plane Block for superior laryngeal nerve blockade.

Three: Research Design, Methods, and Study Steps

1. Research Design

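### For hematoma and infection at the neck injection site, the stated chi-square comparison tests the block arm against an arm that cannot have the event, so it says little about the safety objective (minor).

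*Protocol*

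**What the plan says.** Section Two makes safety a secondary objective: "To assess the safety and ease of performance of ultrasound-guided Thyroid Cartilage Plane Block". It attaches no hypothesis, margin or precision target.

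Section Six, secondary outcome 9, reads: "Record adverse reactions such as local anesthetic toxicity, local hematoma at the puncture site, and infections". Outcomes 6 and 7 add cough, nausea or vomiting, and throat pain.

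Section Eleven does not mention adverse reactions by name. Its rule for categorical data is "Categorical data will be presented as counts or percentages, and group comparisons will be made using the X^2 test", followed by "A significance level of $P<0.05$ will be considered statistically significant". It makes no exception for sparse outcomes or for outcomes that only one arm can have.

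Under Study Steps in Section Three, the control group receives local anesthetic spray through the bronchoscope, and the T group has ultrasound-guided injections on both sides of the neck. On size, Section Three says "Assuming a dropout rate of 10%, the final sample size for each group is determined to be 30 cases".

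**The concern.** A between-arm test is useful when both arms can have the event and the question is whether treatment changes its frequency. A hematoma or infection at a neck injection site cannot arise in patients who have no neck injection. The control count is therefore known in advance to be zero, and the control arm adds no information about that risk. What a reader needs is how often the harm occurs after the block, and how high the rate could be given 30 patients.

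At stake is the meaning of the safety result. The P<0.05 threshold is the only inferential criterion in the protocol. If it is applied to these events, the probable output is a non-significant P value, which could stand in for a safety conclusion while the data remain compatible with a substantial event rate.

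**Working it through.** **Inputs.** From the protocol: 30 per arm (Section Three), Pearson chi-square at 0.05 (Section Eleven; sidedness is not stated, two-sided is assumed), and zero neck-injection events in C (Section Three, Study Steps). Assumed, because the protocol gives no harm rates: true rates of 5% and 10% in T.

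**The plan's own figure.** Section Three states "With a statistical power of $1-\beta=0.9$ and a significance level of $\alpha=0.05$, a sample size of $n=25$ is calculated". This cannot be reproduced, because the pilot rates are not given. The dropout step gives 25/0.9 = 27.8, so 28, against the stated 30. The sizing endpoint is block success, so the sample size was not chosen with harms in mind.

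**Events needed for significance.** With x events in T and 0 in C, the uncorrected statistic is X² = 60·(30x)² / [30·30·x·(60−x)] = 60x/(60−x).

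- x = 3: 180/57 = 3.16, p = 0.076.
- x = 4: 240/56 = 4.29, p = 0.038.

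At least 4 events in T are needed. At 4 against 0 the expected number of events is only 2 per arm, where the chi-square approximation is unreliable. Fisher's exact test gives p = 0.112 there and needs at least 6 events (5 against 0 gives p = 0.052).

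**Exact power.** Because C is fixed at zero, power is the binomial probability P(X ≥ 4) with n = 30.

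- 5%: 1 − (0.2146 + 0.3389 + 0.2586 + 0.1270) = 0.061.
- 10%: 1 − (0.0424 + 0.1413 + 0.2277 + 0.2361) = 0.353 (from unrounded terms).

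Fisher's test gives 0.3% and 7.3% at the same rates.

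**What the T arm alone can say.** Clopper-Pearson two-sided 95% intervals for 30 patients:

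| Events in T | Interval | Pearson p against 0/30 |
|---|---|---|
| 0 | 0% to 11.6% | not computable (no events) |
| 1 | 0.1% to 17.2% | above 0.05 |
| 3 | 2.1% to 26.5% | 0.076 |

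The zero-event limit is 1 − 0.025^(1/30) = 0.116; the one-sided 95% limit is 1 − 0.05^(1/30) = 0.095. The row for 3 events shows the mismatch: the test is not significant, yet the observed rate is 10% and the interval reaches 26.5%.

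**The case against.** The strongest reply is that Section Eleven is a generic paragraph, that it already promises counts or percentages, and that interval methods are commonly left to a statistical analysis plan, which may exist. Section Ten also requires adverse events to be documented, followed and cumulatively reviewed. This is fair as far as it goes. The counts are already planned, and the review in Section Ten serves patient protection. Neither changes the fact that the comparison stated for these outcomes does not suit them. The point is about a rule the protocol does state.

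Some stronger readings are tempting, and the document does not support them:

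- *That a non-significant test will be taken as proof of safety.* No section says so. It is a possible misreading, not a planned inference.
- *That all adverse reactions should be taken out of between-arm testing.* Cough, nausea or vomiting, throat pain and local anesthetic toxicity can occur in both arms, and comparing the arms is reasonable for them.
- *That radial artery hematomas in C would offset neck hematomas in T.* Section Three does say "Perform radial artery puncture and catheter placement" for all patients, and item 9 does not name its site. But item 9 lists the puncture site beside local anesthetic toxicity, which points to the block, and nothing suggests that wrist events would be counted. This justifies clearer wording only.
- *That low power for rare harms is a design error.* It is normal in a trial of 60 patients.

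**Conclusion.** The point holds for neck-injection-site hematoma and infection, which are part of one secondary outcome. For these, the stated test compares T with a structural zero and is close to uninformative: power is 6% at an assumed true rate of 5% and 35% at an assumed 10%, with 30 evaluable patients per arm and an uncorrected two-sided test. The precision figures need no assumed harm rate: 0/30 leaves an upper limit of 11.6%, and 3/30 gives 2.1% to 26.5%. The conclusion also assumes that the puncture site in item 9 means the neck, which is the natural reading. Severity is minor: a secondary objective is affected, and no wrong result follows necessarily from the text.

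**What to change.** 1. In Section Six, item 9, write 'neck injection site' for the hematoma and infection outcomes.
2. In Section Eleven, state that these events are reported in the T group only, as counts with exact (Clopper-Pearson) 95% intervals and no between-arm test.
3. Keep the between-arm comparison for events possible in both arms (cough, nausea or vomiting, throat pain, local anesthetic toxicity), and add a 95% interval for the difference.
4. State that the conclusion on neck-injection safety rests on the upper confidence limit and not on a non-significant P value.

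The cost is a few sentences. It needs no extra patients, visits or procedures. The downside is a more modest safety statement: with no events at all, the trial could say only that the data are compatible with rates up to about 11.6%.
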